#### g) Outcome Determination

Only important ***clinical endpoints and functional outcomes that matter to patients*** will be assessed. The primary effectiveness outcome (benefits) will be the aggregate of all-cause mortality and clinical PE and DVT, confirmed by imaging and resulting in readmission. *Deaths* will be classified either as cardiovascular, if sudden and otherwise unexplained, or caused by myocardial infarction, stroke, arrhythmia, heart failure, pulmonary embolism, or other cardiovascular event. For patients with more than one clinical event, only the first or most serious event will be counted. *Primary safety endpoints* (harms) include major bleeding, clinically important wound and remote bleeding, persistent wound drainage, reoperation for treatment of the wound or removal of the implant for infection, myocardial infarction, and patient-reported function at 4 weeks, 3 months, and 6 months after operation. *Major bleeding* is defined as that which is fatal, occurs in a critical organ or space (retroperitoneal, intracranial, epidural, intraspinal, intraocular, pericardial), results in reoperation, or remote site bleeding that is clinically overt (blood or its breakdown products seen in volume and clinically evident as a collection or mass) and associated with a fall in hemoglobin of at least 2 g/dL, managed with transfusion of two or more units of red blood cells, or prolongs the hospital stay. *Non-major clinically important wound-related bleeding* is defined as persistent drainage beyond 5 days after operation; this increases risk of deep infection and threatens long-term device function. There will be no screening for VTE; diagnostic testing will be performed only for clinical indications. DVT will be diagnosed by loss of compressibility on venous ultrasound or evidence of a filling defect on invasive contrast venography. PE will be diagnosed on the basis of contrast-enhanced chest computed tomography, ventilation-perfusion lung scanning, or pulmonary angiography. Myocardial infarction will be diagnosed by laboratory-defined elevation in troponin and/or appropriate changes on electrocardiogram. *Suspected VTE-related clinical events will not be counted unless confirmed by diagnostic imaging.* Audit of pertinent events will occur at the time of enrollment in the study, at hospital discharge, and 4 weeks, 3 months, and 6 months after operation. All endpoints will be adjudicated by investigators (OAC) who are unaware of patient group assignments.

## 3.1.2.1. Schedule of Events

	Screening	Baseline (-3 months to -1 day)	Randomization (Surgeon Confirmation to -1 day)	Surgery (Day 0)	Post Op (Day 1)	Hospital Discharge	4 Week FU (+ 10 days)	3 Month FU (+/- 10 days)	6 Month FU (+/- 1 month)
Pre-Screen Form	X								
Screening Form	X								
Eligibility Review	X								
Electronic/ Written Informed Consent		X							
HOOS/KOOS		X					X	X	X
Oswestry Instrument		X							
Charlson Comorbidity Index		X							
PROMIS-10 Global Health Survey		X					X	X	X
Randomization			X						
Urine Pregnancy Test				X*					
Study Drug Administration (Aspirin Arm)				X (ongoing for 30 days)	X	X	X		
Study Drug Administration (Rivaroxaban Arm)				X (ongoing for 30 days)	X	X	X		
Perioperative Form						X			
AE/SAE Monitoring			X	X	X	X	X	X	X

\* Urine pregnancy test done as part of the patient's standard of care and the results will be reviewed for research purposes.

## 3.1.3. Data Analysis

Primary Data Analysis

The unblinded nature of the clinical trial could threaten unbiased comparisons. Randomized patients will not be notified of treatment group assignment until the day of the proposed operation, unless necessary to provide third party insurance coverage for prescribed medical care. Further, our trial is protected from this threat to adherence with treatment assignment by the short course of treatment, the follow-up contact to ascertain treatment, and the motivation of each patient to take prescribed drugs to prevent PE and DVT. The trial is protected from the threat to unbiased outcome ascertainment and classification by the independent centralized contact with patients to determine need for collection of clinical documents, preparation of documents related to readmission or treatment for bleeding or thrombosis to remove any indication of treatment assignment, and blinded outcome classification based upon expert review of the redacted documents by the OAC.

**1.0 Primary Aim 1.** *To compare the frequency of the aggregate clinical endpoint of important venous thromboembolism (clinical PE and DVT leading to hospital readmission) and all-cause mortality.*

**1.1 Risk Estimates.** First, 6-month probabilities of our primary composite endpoint (clinical PE, clinical DVT, and all-cause mortality) by treatment group will be estimated and compared. To address the fact that some participants will have incomplete follow-up (e.g., we may know whether they had an event within 3 months but not for the full 6 months), we will estimate 6-month risk of an event using a Kaplan-Meier approach. Confidence intervals will be based on Greenwood's formula (applied using the delta method to a complementary log-log transformation of the estimated risk). In these calculations, those whose follow-up is incomplete will be censored at the time that the follow-up ends.

The **primary analysis will be a "per-protocol analysis"**. In this analysis, patients will be censored at the time that they switch away from the treatment to which they were randomized. Thus, for example, if a patient was randomized to rivaroxaban and was treated with aspirin instead, they will not be included in the per-protocol analysis. If a patient received the treatment to which they were randomized, but later switched treatments, the patient will be included in the per-protocol analysis up until the time the patient switched, and then censored (as recommended by Hernan and Robins, NEJM, 377:14, 1391-1398).

Note that in our “per protocol analysis”, we will still include patients in the analysis who do not completely and fully adhere to the medicine to which they are assigned and treated. Thus, for example, if a patient is randomized to, and treated with, aspirin in the hospital but reports failing to take aspirin in the four weeks after hospital discharge, they will still be included in the analysis. This is because this is a pragmatic trial and the goal is to estimate the risks in a real-world setting. Specifically, our goal is to estimate the risks among those who are prescribed and have access to a particular medication. We recognize that this use of the expression “per-protocol analysis” is not a traditional one, which would typically exclude all those who do not fully adhere to their medication, and can result in a study sample that is not perfectly representative of the study population as a whole. We believe that this lack of representativeness is more acceptable than the bias that would be incurred in an intention-to-treat analysis which would include patients who are not treated with a medication in an analysis of risks among those taking that medication.

In secondary analyses, we will also perform an intention to treat analysis and an “as-treated” analysis. In the intention to treat analysis, patients will be included in the analysis in the group to which they were randomized and only be censored when they are lost to follow-up. However, some patients who are randomized will be excluded from all analyses (See sections 1.3 and 1.4 below). In the “as treated” analysis, patients will be included in the group based on the study medication they actually received. Thus, for example, if a patient is randomized to rivaroxaban but receives aspirin, they will be included in the aspirin group. This approach will include “crossover” patients and provide more precise estimates of what actually happened to patients who took the study medications, but will need to be interpreted with caution as this approach has more potential to result in a lack of representativeness of the groups.

**1.2 Treatment Comparisons.** Next, each pairwise comparison of the treatment groups (i.e., aspirin vs. rivaroxaban, aspirin vs. warfarin, rivaroxaban vs. warfarin) will be performed separately, only including those patients with no medical contra-indication for either of the two treatments in that pair. In addition, for each pairwise comparison, we will only include those patients who were randomized at sites during a period of time where patients could have been randomized to either of the two treatments being compared. For example, a patient randomized to aspirin at a site restricted to use of rivaroxaban and aspirin cannot be included in an aspirin to warfarin comparison because that patient could not have received warfarin at their respective site (see below).

For each pairwise comparison we will calculate a two-sided 95% confidence interval for the risk difference (i.e., the difference between the groups with respect to risk of the composite endpoint) based on the variances of each estimated 6-month risk calculated by Greenwood’s formula. These confidence intervals will be interpretable as the range of differences that cannot be ruled out by a test at the two-sided 5% level. Next, the strength of evidence for non-inferiority of aspirin relative to rivaroxaban with respect to risk of our primary endpoint will be formally assessed by calculating a one-sided p-value for the null hypothesis that the 6-month risk of an event among those in the aspirin group is at least 0.69 percentage points greater than the risk among patients taking rivaroxaban. A low p-value indicates evidence against this hypothesis and would suggest that the risk among those taking aspirin is less than 0.69 percentage points greater than the risk among those taking rivaroxaban. The p-value will be based on the test statistic:

$$= \frac{\hat{r}_{\text{aspirin}} - \hat{r}_{\text{rivaroxaban}} - 0.0069}{\sqrt{\text{VAR}(\hat{r}_{\text{aspirin}}) + \text{VAR}(\hat{r}_{\text{rivaroxaban}})}}$$

where  $\hat{r}_{\text{aspirin}}$  is the estimated risk of events in the aspirin group and  $\hat{r}_{\text{rivaroxaban}}$  is the estimated risk in the rivaroxaban group. The p-value will be the probability that a standard normal random variable will be less than this value. Note, a one-sided test (rather than a two-sided test) is appropriate for evaluation of a non-inferiority hypothesis and is recommended by Farrington and Manning. An analogous statistic will be calculated to compare aspirin to warfarin.

The standard analysis for superiority trials is to base the analysis on the principle of intention to treat. In this analysis, patients are included in the group to which they were randomized, irrespective of the treatment actually received. However, as recognized by the FDA in their guidance, in a non-inferiority analysis, the intention-to-treat analysis is biased towards finding non-inferiority because protocol violations and cross-overs tend to diminish

 <https://www.fda.gov/downloads/Drugs/Guidances/UCM202140.pdf>

differences between groups. Therefore, similar to the estimation of risks, the primary analysis of non-inferiority will be based on only on follow-up while patients were treated with the medication to which they were randomized (a per-protocol analysis). We do recognize, however, that the exclusion or censoring of randomized patients from the analysis due to medication switching could result in differences between the groups that will bias their comparisons. To address this possibility, in secondary analyses, the patients will be weighted to adjust for imbalances between the groups with respect to age, sex, site, and education, as described in section 1.5.4 below.

The two-sided confidence interval for the treatment differences will also be used to assess superiority of one treatment over another. If the confidence interval does not overlap 0, then this would be equivalent to statistically significant superiority of one treatment over another at the two-sided 0.05-level. A p-value to summarize the strength of evidence against the null hypothesis that the risk is equal in the two groups can be calculated based on the Z-statistic:

$$= \frac{\hat{r}_{Rx1} - \hat{r}_{Rx2}}{\sqrt{VAR(\hat{r}_{Rx1}) + VAR(\hat{r}_{Rx2})}}$$

where the risks and variances are calculated using the Kaplan-Meier approach and Greenwood's formula.

Finally, comparisons of a composite of the primary effectiveness endpoint, prevention of thromboembolic events, *and* the primary safety endpoint, avoidance of bleeding-related events, will be performed among the three treatment groups. This assessment of "net clinical benefit" (Samama CM et al, NEJM 2020 May 14;382:1916-1925) will consist of comparing a combined measure, the percentage of patients with either a primary effectiveness endpoint (symptomatic DVT and PE plus all-cause mortality) or a primary safety endpoint (aggregate of bleeding complications including major, non-major clinically important, and wound-related) between each pair of treatments. Analyses will be conducted in the same manner as described above.

**1.3 Randomized patients who do not undergo surgery.** Patients who were randomized but then do not undergo surgery will be excluded from all analysis. This approach is consistent with the recommendations of Fergusson et al, BMJ. 2002 Sep 21;325(7365):652-4.

**1.4 Study events that occur before surgery.** Outcome events that occur after randomization but before surgery will not be counted as events in this study because the study concerns post-surgery events.

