#### d) Randomization

Randomization of consented patients occurs after the surgeon confirms eligibility and up until the day before the originally scheduled surgery date. If a patient's surgery is postponed, or cancelled and ultimately rescheduled, the patient will keep the original randomization assignment. The ability to randomize a patient will be available via the web-based randomization system once consent has been signed and all baseline instruments have been entered into the database. Study group assignments will be shared with the surgeon at the time of randomization, and with the patient on the day of operation unless necessary to provide third party insurance coverage for prescribed medical care.

Patients will be assigned to treatment groups using a web-based randomization system. A permuted block randomization scheme will be utilized to ensure equal assignment of patients to each drug study group at each participating site, taking into consideration the noted criteria for stratified randomization. In the absence of any randomization stratification requirements, patients meeting all eligibility criteria without any randomization exclusions will be assigned to one of two groups; a concealed centralized randomization schedule will provide assignment to one of two prophylaxis regimens (aspirin or rivaroxaban) in randomly varying block sizes developed separately for each clinical site and stratified according to type of surgery (hip or knee replacement). Prophylaxis will continue for 30 days, in accordance with clinical guidelines, and pneumatic compression devices will be utilized in hospital in conjunction with both of the treatment groups according to local practice. The two groups are as follows:

- 1) Enteric coated aspirin (regimen with lowest bleeding risk; clinical PE and all-cause mortality rates comparable to more intensive anticoagulants); and
- 2) Rivaroxaban, an oral direct Factor Xa inhibitor (regimen with lowest PE and DVT rate but higher bleeding risk [3-5%]).

A contraindication to one of the two study prophylaxis regimens for venous thromboembolism is exclusionary. The contraindications to aspirin are:

- 1) Patients with a known aspirin allergy;
- 2) Patients with a personal history of PE or DVT;

- 3) Patients with a known condition of thrombophilia proven by diagnostic testing; e.g. Factor V Leiden;
- 4) Patients with a cancer diagnosis who are under active treatment.

The contraindications to rivaroxaban are:

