the groups that can confound comparisons. Therefore, in a secondary analysis, we will adjust for these imbalances using weights. Specifically, we will calculate an adjusted Kaplan-Meier estimate using the method described by Xie and Liu (2005, *Statistics in Medicine* 24:3089:3110). This is an approach that involves weighting each observation by the inverse probability of being in one group (vs. the other group) when calculating the Kaplan-Meier estimates. Candidate variables for weighting will include age, sex, site, date of surgery, and education. Weights will be derived so that, after weighting each participant, the groups will be comparable with respect to the proportion of follow-up in each subgroup defined by the covariates. This will effectively remove confounding due to imbalances between the groups with respect to these measured covariates. These adjusted Kaplan-Meier estimates can be calculated in SAS 9.4.

This approach will result in unbiased estimates if the data are “missing at random” (i.e., missingness may depend on observed patient characteristics but not on the outcome). To address the possibility that the data are “missing not at random” we will perform some sensitivity analyses. One sensitivity analysis will be to perform an intention-to-treat analysis after excluding the sites with the greatest cross-over rates. Another would be to assess impact of various degrees of departure from the missing-at-random assumption on the qualitative conclusions using methods described by [name] LS. (*Control Clin Trials*. 2003 Aug;24(4):411-21) or by Kim et al (Kim M, Wang C, Xue X. (2019) *Stat Med* 38:650-659). However, these methods are designed for binary data and will have to be adapted to time-to-event data that we will use as our outcome.

**2.0 Primary Aim 2.** *To compare the frequency and nature of bleeding complications (major, clinically important, and wound-related bleeding) leading to persistent wound drainage, reoperation, deep infection, or myocardial infarction.*

Using the same methods as described for Aim 1, 6-month probabilities of our primary composite safety endpoint inclusive of bleeding complications by treatment group will be estimated and compared. The primary analysis will be a per-protocol analysis for as described above for Aim 1. Sensitivity analyses for missing outcomes will be performed as described above for Aim 1.

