**3.0 Primary Aim 3.** *To compare patient-reported outcomes (PRO) in patients experiencing primary effectiveness and safety endpoints in order to assess the impact of such events on specific function of the replaced joint as well as general patient well-being.*

**3.1 Analysis Plan.** The primary patient-reported outcomes will be the HOOS, JR. (hip disability and osteoarthritis outcome score), the KOOS, JR. (Knee injury and osteoarthritis outcome score) and the PROMIS-10 measure of global health. The questions needed to calculate these scores will be asked at each time point (baseline, 1 month, 3 months and 6 months after surgery). These measures will be scored as recommended by the developers. The treatment groups will be compared with respect to the distribution of these scores at each time point. Formal inference regarding the impact of treatment on the changes in these scores will be performed using a general linear model. This will be fit using an unstructured covariance structure to allow a different variance at each time point and different covariances between each pair of time points. The model will include terms representing the mean outcome at each treatment/time/eligibility stratum combination.

In addition, we will compare the treatment groups with respect to specific items used to compute the HOOS, JR and KOOS, JR. For the KOOS, JR, we pre-specify interest in comparing the groups with respect to the following three questions:

1. How severe is knee stiffness after first waking in the morning?
2. What is the degree of difficulty when rising from sitting?
3. What is the degree of difficulty when bending to floor to pick up object?

For the HOOS, JR we pre-specify interest in the following two questions:

1. What is the degree of difficulty when rising from sitting?
2. What is the degree of difficulty when bending to floor to pick up object?

To assess the association between thromboembolic or bleeding complications and patient reported outcomes of function, pain, or quality of life, we will use models similar to those described above. We will add terms to the models representing the experience of a previous thromboembolic or bleeding complication.

As for Aims 1 and 2, the primary analysis will be based on the per-protocol follow-up with secondary analyses based on the intention-to-treat approach and the as-treated approach.

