**Table 1. Numbers of patients and resulting power and precision in comparing aspirin to warfarin.**

	Aspirin	Warfarin
Number Randomized as of May 1, 2023	5132	5389
Number Eligible for both treatments (either medically or due to logistics)	4703	4698
Projected number who took the assigned treatment 	4402	3688
Projected number who will have complete follow-up 	3962	3319
Projected width of the 95% CI for the difference in risk of primary outcome	0.96 percentage pts	
Power to obtain evidence of non-inferiority based on 0.69% margin of inferiority	80.3%	
Margin of inferiority detectable with 80% power	0.69 percentage pts	

Based on a crossover rate of 21.5% and 6.4% for Warfarin and Aspirin, respectively.

Assuming that 90% of those randomized have surgery, do not withdraw, and have 6-month follow-up information.

**Recruitment and randomization.** To achieve the total of approximately 18,000 evaluable patients we will recruit approximately 20,000 to accommodate the possibility of 10% loss to follow-up. We will randomize patients with equal probabilities to each of the three regimens using a web-based program provided by Statix. Those sites that are on the restricted randomization plan due to structural barriers will randomize patients using a 1:1 randomization scheme. Following removal of warfarin from the protocol in June 2023, all sites will randomize patients using a 1:1 scheme to either aspirin or rivaroxaban. The web application is available 24/7, password protected, and maintains an audit trail of transactions with time stamp login for users. There will be a separate randomization schedule for each clinical site, stratified according to operation (hip or knee) to ensure balanced intervention groups with respect to site and operation. Within each stratum, assignments will be randomly permuted within repeating blocks of varying size.

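### Randomisation is stratified by site and operation, but the primary per-protocol risk difference is not, so site-dependent crossover can bias it

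*Protocol*

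**What the plan says.** Protocol 3.1.2 d) and the recruitment and randomization paragraph after Table 1 give each site its own schedule, split by hip or knee, with permuted blocks. The stated purpose is "to ensure balanced intervention groups with respect to site and operation".

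Protocol 3.1.3, section 1.2, then writes the primary analysis out in full: "we will calculate a two-sided 95% confidence interval for the risk difference", "based on the variances of each estimated 6-month risk calculated by Greenwood’s formula". Non-inferiority is judged by "calculating a one-sided p-value for the null hypothesis" that aspirin is at least 0.69 points worse. The statistic is the difference of two whole-arm Kaplan-Meier risks, less 0.0069, over the root of the summed variances. The superiority Z has the same form, the warfarin comparison uses an analogous statistic, and section 2.0 applies the same methods to Aim 2. Site and operation appear in none of them.

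Section 1.1 makes the per-protocol set primary: patients never treated as assigned are left out and later switchers are censored. Section 1.2 concedes that this may bias the comparison and answers with a secondary weighted analysis. The candidate weights in 1.5.4 include site and date of surgery but not operation. The same section plans an intention-to-treat sensitivity analysis "excluding the sites with the greatest cross-over rates". Section 4.2 repeats the methods separately for hip and knee under a secondary aim. For patient-reported outcomes, section 3.1 states: "The model will include terms representing the mean outcome at each treatment/time/eligibility stratum combination".

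**The concern.** Blocking balances the arms within each site and operation only among the patients randomised. The primary set is what remains after treatment-related exclusion, and that exclusion is heavier in the comparator arms than on aspirin. The reasons for crossover given in 3.1.2 d), cost and surgeon discretion, can plausibly differ between hospitals, and the planned exclusion of high-crossover sites shows that the protocol expects this.

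A site where many comparator patients cross over contributes fewer comparator than aspirin patients to the primary set. If that site's underlying event risk is above or below average, the crude whole-arm difference picks up part of the site difference as if it were a treatment effect. At stake is the verdict on a 0.69-point margin, most of all against warfarin, where the planned power is only 80.3%.

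**Working it through.** **1. The plan's own figure.** Inputs: event risk p = 1.1% (section 5.2); 3962 aspirin and 3319 warfarin patients with complete follow-up, margin 0.69 points (Table 1).

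SE = √[0.011 × 0.989 × (1/3962 + 1/3319)] = 0.245 points.

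- CI width: 2 × 1.96 × 0.2454 = 0.962 points (stated 0.96).
- Power: Φ(0.69/0.2454 − 1.96) = 80.3% (stated 80.3%).
- Margin at 80% power: (1.96 + 0.8416) × 0.2454 = 0.688 (stated 0.69).

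The level of the one-sided test is not stated; 0.025 reproduces Table 1, while 0.05 gives 87.8%. The power figure is thus that of an unstratified test at one-sided 0.025.

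**2. Precision.** Stratifying removes a fraction f = [⅓(p_hip − p)² + ⅔(p_knee − p)² + (CV × p)²] / [p(1 − p)] of the variance. The 1:2 hip:knee split is the protocol's. Assumed, because the protocol gives neither: a knee:hip risk ratio of 1 to 3 and a between-site CV of risk of 0 to 0.75. Then f runs from 0% to 0.81%, the CI width falls to 0.958 points at best, and power rises to at most 80.6%. This is negligible.

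**3. Bias, two-group model.** Assume half the sites have risk p(1 − c) and half p(1 + c), with c = 0.25 to 0.5. Comparator crossover is x(1 − s) in one half and x(1 + s) in the other, with s = 0.5 to 1, and aspirin crossover is uniform. The shift in the crude difference is p·c·x·s/(1 − x).

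Crossover x is 21.5% for warfarin (Table 1) and 13.6% for rivaroxaban (section 5.1). These two places give different figures for aspirin (6.4% and 2.5%) and for warfarin; each is used here only for its own comparison. The rivaroxaban SE is √[0.011 × 0.989 × (1/6515 + 1/6501)] = 0.183 points, from 90% of the 7239 and 7223 in section 5.1.

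| Comparison | c, s | Shift (points) | Share of margin | One-sided error at the margin if it favours aspirin |
|---|---|---|---|---|
| Warfarin | 0.25, 0.5 | 0.038 | 5.5% | 3.5% |
| Warfarin | 0.25, 1 or 0.5, 0.5 | 0.075 | 10.9% | 4.9% |
| Warfarin | 0.5, 1 | 0.151 | 21.8% | 8.9% |
| Rivaroxaban | 0.25, 0.5 | 0.022 | 3.1% | 3.3% |
| Rivaroxaban | 0.5, 1 | 0.087 | 12.5% | 6.9% |

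The error column is Φ(shift/SE − 1.96), against a nominal 2.5%. For warfarin, a 0.075-point shift moves power from 80.3% to 70.7% if it works against aspirin and to 87.7% if it works for it.

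**4. Bias, correlation model (rivaroxaban).** Shift = correlation × SD(risk) × SD(retention) / 0.864. With assumed values 0.2, 0.3 points and 0.1 it is 0.007 points. With 0.5, 0.5 points and 0.2 it is 0.058 points. The error becomes 2.7% and 5.0%. Using instead the SE implied by the 0.27 and 0.30 margins of error in section 5.2, √(0.27² + 0.30²)/1.96 = 0.206, the upper figure is 4.7%.

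**5. Operation alone.** With a 10-point hip/knee gap in comparator crossover and a risk ratio of 2, the shift is 0.019 points for warfarin and 0.017 for rivaroxaban. Site is the larger concern.

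**The case against.** The strongest reply is that the protocol has already seen this. It admits the bias, plans a Kaplan-Meier analysis weighted for site, adds intention-to-treat analyses free of exclusion for switching, and analyses hip and knee separately. What remains is whether adjustment should be primary or secondary. The between-site figures are not in the document, the sign is unknown, and the large errors need the extreme assumptions. All of that is fair and keeps the point small. It does not remove it: every safeguard is secondary, the test that decides non-inferiority is the unadjusted one, and the weights omit one of the two randomisation factors.

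Sparse strata are also raised. About 25 sites by two operations gives some 50 strata, or about 6515/50 = 130 patients and 1.1% × 130 = 1.4 events per stratum and arm for rivaroxaban (equal strata assumed). Many strata will have no events. Weights that depend on patient counts only, with summed variances, tolerate this, and standardisation or weighting avoids it.

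Some stronger readings are not supported. A reader might infer a material loss of precision in the primary test; step 2 shows there is none. A reader might infer that ignoring the strata inflates type I error by itself; under intact randomisation it does not. Nor does the patient-reported outcome analysis ignore both factors: HOOS, JR and KOOS, JR are joint-specific, so operation is unseparated only for PROMIS-10. Baseline is also among the modelled time points, so stable site differences largely cancel from changes in score.

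**Conclusion.** The point holds as a minor one, on grounds of bias. The primary difference is not held within the randomised strata, and unequal per-protocol exclusion means that balance within them is no longer guaranteed. The possible shift is about 0.01 to 0.09 points against rivaroxaban (1% to 13% of the margin) and 0.04 to 0.15 points against warfarin (5% to 22%), in either direction.

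These sizes rest wholly on assumed between-site variation in risk and crossover, and on the two being related; if they are unrelated, the shift is zero. The documents do not show that the bias exists or which arm it favours. They show that the primary test is open to it and that the variables needed to guard against it are already held for randomisation.

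**What to change.** In section 1.2, and so by reference in Aim 2, make the primary 6-month risk difference stratified by or standardised to site and operation, within the same 0.69-point test. Either form would do:

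- Within-stratum Kaplan-Meier differences combined with Mantel-Haenszel weights n₁n₂/(n₁ + n₂) and the matching summed variance, with a prespecified rule for pooling small sites.
- The weighted Kaplan-Meier of section 1.5.4 with operation added, promoted to primary.

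Keep the crude difference as a sensitivity analysis. Add operation to the 1.5.4 weights in any case. Optionally, add site to the patient-reported outcome models and operation to the PROMIS-10 model; the gain there is probably small and cannot be quantified from the protocol.

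The cost is a few lines of text and code. Three limits should be stated. Strata will be sparse. Mantel-Haenszel weights on retained patients give less weight to high-crossover sites, which shifts the target population somewhat. And neither form protects against switching related to a patient's own risk within a stratum, beyond what measured covariates capture, so the intention-to-treat analysis stays necessary.
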